#### 9.7.4 Sequence of Analyses

The main analysis will be performed once the study is completed with the purpose of evaluating all outcomes and database is locked.

#### 9.8 Quality Control

Quality control activities will include verification of data and ensure the data collected in the eCRF is accurate, valid and in accordance with the protocol. Only authorized staff will have access to the Electronic Data Capture system via a secure website and will receive training regarding data entering in the eCRF.

Representatives of Sponsor and/or its delegates must be allowed to visit all study site locations to assess the data quality and study integrity. On site, they will review study files and, if allowed by local laws and regulations, subject medical charts to compare them with source documents, discuss the conduct of the study with the investigator, and verify that the facilities remain acceptable.

In addition, the study may be evaluated by Sponsor internal auditors and government inspectors who must be allowed access to case report forms (CRFs), source documents, other study files, and study facilities. The investigator must notify Sponsor promptly of any inspections scheduled by regulatory authorities, and promptly forward copies of inspection reports to Sponsor.

## **9.9 Limitations of the Research Methods**

This study is open label and observational, and data are abstracted from medical records. There is limited control over patient assessment as patient monitoring and diagnostics are per standard of care. This may result in missing data. In addition, variability in the treatments received may limit interpretation of the results (e.g., decreased adherence to, or early discontinuation of cladribine tablet treatment courses, or potential interaction with medication for other conditions). Patient specific methodological challenges such as potential biases from patient selection and loss to follow-up of patients through study attrition are also other limitations. Furthermore, the inclusion/exclusion criteria of the study limit the study population to patients who are alive at least 3 years after cladribine tablet treatment initiation and are able to provide informed consent; consequently, patients who have passed away after cladribine tablet treatment initiation are excluded. In addition, the first-year treatment course must have been completed by the patients, thus patients who discontinued treatment due to, for instance, an immediate adverse drug reaction will be excluded from participation.

## **9.10 Other Aspects**

### **9.10.1 Independent Ethics Committee or Institutional Review Board**

Prior to commencement of the study at a given site, the protocol will be submitted together with its associated documents (specify which documents, e.g., consent form) to the responsible Independent Ethics Committee (IEC) for its favourable opinion/approval. The written favourable opinion/approval of the IEC will be filed by the investigator and a copy will be sent to the Sponsor.

The study must not start at a site before the Sponsor has obtained written confirmation of favourable opinion/approval from the concerned IEC and R&D approval is in place at the site level. The IEC will be asked to provide documentation of the date of the meeting at which the favourable opinion/approval was given, and of the members and voting members present at the meeting. Written evidence of favourable opinion/approval that clearly identifies the study, the protocol version, and the Patient Information and Consent Form version reviewed should be provided. Where possible, copies of the meeting minutes should be obtained.

Amendments to the protocol will also be submitted to the concerned IEC/IRB before implementation in case of substantial changes.

## 9.10.2 Monitoring

This trial will be monitored in accordance with the ICH GCP, and any other applicable regulations. The site Monitor will perform study visits to the trial site or remotely at regular intervals.

## 9.10.3 Health Authorities

As chart review study, no approval is required from the National Health Authorities, as in accordance with the regulations of the UK.

## 9.10.4 Quality Assurance

In compliance with regulatory requirements, the Sponsor, a third party on behalf of the Sponsor, regulatory agencies, or IECs may conduct quality assurance audits/inspections at any time during or following a study. The investigator must agree to allow auditors/inspectors direct access to all study-related documents, including source documents, and must agree to allocate his or her time and the time of his or her study staff to the auditors/inspectors in order to discuss findings and issues.

The protocol, each step of the data capture procedure, and the handling of the data, as well as the study report, may be subject to independent Clinical Quality Assurance. Audits may be conducted at any time during or after the study to ensure the validity and integrity of the study data.

## 9.10.5 Archiving

The archive should be maintained for the period specified by local regulations, where applicable. All original patient files (medical records) must be stored at the site (hospital, research institute, or practice) for the longest possible time permitted by the applicable regulations. In the absence of applicable regulations, the archive should be maintained for at least 5 years after the final study report or the first publication of study results, whichever comes later. In any case, the investigator should ensure that no destruction of medical records is performed without the written approval of the Sponsor.

# 10 Protection of Human Subjects

## 10.1 Subject Information and Informed Consent

An unconditional prerequisite for a patient's participation in the study is his/her written informed consent. The patient's written informed consent to participate in the study must be given before any study-related activities are carried out.

Adequate information must therefore be given to the patient by the investigator before informed consent is obtained (a person designated by the investigator may give the information, if permitted by local regulations). A patient information sheet in the local language will be provided by the Sponsor for the purpose of obtaining informed consent. In addition to providing this written information to a potential participant, the investigator or his/her designee will inform the patient verbally of all pertinent aspects of the study (*the language used in doing so must be chosen so that*

---

*the information can be fully and readily understood by laypersons).* Depending on national regulations, a delegate assigned by the investigator may inform the subject and sign the Informed Consent Form.

The Informed Consent Form must be signed and personally dated by the patient and the investigator. The signed and dated declaration of informed consent will remain at the investigator's site and must be safely archived by the investigator. A copy of the signed and dated information and consent form should be provided to the patient prior to participation.

In case of remote consent, the site will contact the patient by phone to explain the study and will send the Information sheet and Informed Consent Form to the patients who have interest to participate. Patients will have the opportunity to ask questions over the phone and will be given sufficient time to decide whether they would like to participate. It will be clear that participation is voluntary, and the patients will be able to decide freely if they wish to participate. If the patient is willing to participate, informed consent will be provided by phone and by written consent. The medical records of the patients will need a statement that informed consent was obtained before starting the data collection. The informed consent procedure will meet requirements of local regulations.

Whenever important new information becomes available that may be relevant to the patient's consent, the written patient information sheet and any other written information provided to patients will be revised by the Sponsor and be submitted again to the IEC for review and favourable opinion. The agreed, revised information will be forwarded to each patient in the study. The investigator will explain the changes to the previous version.

## **10.2      Subject Identification and Privacy**

When a patient is enrolled (i.e., informed consent is provided), the investigator will assign a unique subject number. This number will serve as the patient's identifier in the study as well in the study database.

Only authorized persons will have access to identifiable personal details, if required for data verification. The patient's original medical data that are reviewed at the site during source data verification by the Monitor, audits, and Health Authority inspections will be kept strictly confidential. The investigator agrees to provide direct access to these documents to the Sponsor and to Health Authority representatives. The investigator is responsible for retrieving information from personal medical records.

Data protection and privacy regulations will be observed in capturing, forwarding, processing, and storing patient data. Patients will be informed accordingly and will be requested to give their consent on data handling procedures in accordance with national regulations.

## 11 Adverse Events

### 11.1 Definitions

An AE is any untoward medical occurrence in a patient or clinical study subject administered a pharmaceutical product and which does not necessarily have a causal relationship with this treatment. An AE can therefore be any unfavourable and unintended sign (including an abnormal laboratory finding), symptom, or disease temporally associated with the use of a medicinal product, whether or not considered related to the medicinal product.

Investigators should assess the severity/intensity of any AE as follows:

**Mild:** The subject is aware of the event or symptom, but the event or symptom is easily tolerated.

**Moderate:** The subject experiences sufficient discomfort to interfere with or reduce his or her usual level of activity.

**Severe:** Significant impairment of functioning: the subject is unable to carry out usual activities.

A serious adverse event is any AE as defined above, which also fulfils at least one of the seriousness criteria below:

- Results in death
- Is life-threatening
- Requires in-patient hospitalisation or prolongation of existing hospitalisation
- Results in persistent or significant disability/incapacity
- Is a congenital anomaly/birth defect
- Is otherwise considered as medically important

 Life-threatening in this context refers to a reaction in which the patient was at risk of death at the time of the reaction; it does not refer to a reaction that hypothetically might have caused death if more severe.

 Medical and scientific judgement should be exercised in deciding whether other situations should be considered as serious reactions, such as important medical events that might not be immediately life-threatening or result in death or hospitalisation but might jeopardise the patient or might require an intervention to prevent one of the other outcomes listed above. Such important medical events should be considered as serious.

Examples of such events are intensive treatment in an emergency room or at home for allergic bronchospasm, blood dyscrasias or convulsions that do not result in hospitalisation or development of dependency or abuse. As a guidance, the important medical event terms list is intended to be used for assessment of suspected adverse reactions (see EMA/207865/2017).

---

Any suspected transmission via a medicinal product of an infectious agent is also considered a serious adverse reaction.

## **11.2 Management and Reporting of Adverse Events**

In this study, safety data collection is based on secondary use of pseudo-anonymised data from existing patient records. Any AEs will be abstracted from the patient records, regardless of seriousness or relationship to cladribine tablets, from the date of initiation of treatment with cladribine tablets until the end of the study period.

Reports of the selected AEs (as listed in [Section 9.1.2.2](#)) will be summarised in the final study report(s).

The investigator will comply with UK pharmacovigilance requirements as defined by HMR (Part-11) to spontaneously report appropriate safety data to the Medicines and Healthcare products Regulatory Agency (MHRA) (e.g., Yellow Card Scheme) as applicable or directly to Merck Serono Ltd.

## **12 Plans for Disseminating and Communicating Study Results**

### **12.1 Study Report**

The completed study will be summarised in a final report that accurately and completely presents the study objectives, methods, results, limitations of the study, and interpretation of the findings.

### **12.2 Publication**

The first publication will be a publication of the results of the analysis of the primary outcomes that will include data from all study sites.

The investigator will inform the Sponsor in advance about any plans to publish or present data from the study. Any publications and presentations of the results (abstracts in journals or newspapers, oral presentations, etc.), either in whole or in part, by investigators or their representatives will require pre-submission review and approval by the Sponsor.

The Sponsor will not suppress or veto publications but maintains the right to delay publication in order to protect intellectual property rights.

## 13

10	Study Participants	14
10.1	Disposition of Participants and Discontinuations.....	14
10.2	Protocol Deviations / Exclusion from Analysis Sets.....	15
10.2.1	Important Protocol Deviations.....	15
11	Demographics and Other Baseline Characteristics.....	16
11.1	Demographics	16
11.2	Medical History and Comorbidities.....	16
12	Previous or Concomitant Therapies/Procedures.....	17
13	Exposure	17

14	Effectiveness.....	18
14.1	Primary Outcome: ARR.....	18
14.1.1	Primary Objective: Derivation and analysis of the primary outcome: ARR	18
14.2	Secondary Outcomes	18
14.2.1	Secondary Objective: Derivation and analysis of the secondary outcome: RFR.....	18
14.2.2	Secondary Objective: Derivation and analysis of the secondary outcome: Treatment discontinuation	19
14.2.3	Secondary Objective: Derivation and analysis of the secondary outcome: Subsequent DMTs.....	19
14.2.4	Secondary Objective: Derivation and analysis of the secondary outcome: EDSS and disability progression	20
15	Safety Analyses	21
15.1	Adverse Events	21
15.1.1	All Adverse Events	21
15.2	Clinical Laboratory Evaluation.....	23
16	Other Outcome MRI Lesions.....	24
16.1	Other Outcome MRI Lesions: Derivation and analysis of the Other Outcome MRI Lesions.....	24
17	References.....	25

2

List of Abbreviations and Definition of Terms

AE – Adverse event

ARR – Annualised relapse rate

CI – Confidence interval

CRF – Case report form

CSR – Clinical study report

eCRF – (electronic) Case Report Form

DMT – Drug modifying therapy

EDSS – Expanded disability status scale

ENR – Enrolled Analysis Set

FAS – Full Analysis Set

IAP – Integrated Analysis Plan

IPD – Important protocol deviations

KM – Kaplan-Meier

MedDRA – Medical Dictionary for Regulatory Activities

PT – Preferred Term

RFR – relapse-free rate

SCR – Screening analysis set

SD – Standard deviation

SOC – System Organ Class

TEAE – Treatment-Emergent Adverse Event

TEAESI – TEAE of Special Interest

TFL – Time to first lesion

3 Modification History

Unique Identifier for Version	Date of IAP Version	Author	Changes from the Previous Version
1.0	17SEP2021	PPD	First version
2.0	15DEC2022		Removal of references to the interim analysis Revision of medical history and comorbidities definitions Revision of previous therapies and procedures definition
3.0	12SEP2023		Inclusion of additional courses of cladribine treatment after Year 2 Revision of imputation rules for partial dates Addition of chart review 2 timing to patient disposition Updated section 15.2 to add grades of lymphocyte counts Updated section 14.2.2 for definition of treatment discontinuation

4 Purpose of the Integrated Analysis Plan

The purpose of this Integrated analysis plan (IAP) is to document technical and detailed specifications for the analysis of data collected for protocol MS700568-0150. Results of the analyses described in this IAP will be included in the final clinical study report (CSR). Additionally, the planned analyses identified in this IAP may be included in regulatory submissions or future manuscripts. Any post-hoc, or unplanned analyses performed to provide results for inclusion in the CSR but not identified in this prospective IAP will be clearly identified in the CSR.

The IAP is based upon Section 9.7 (Data Analysis) of the study protocol and protocol amendments and is prepared in compliance with ICH E9. It describes analyses planned in the protocol and protocol amendments.

5 Objectives and Endpoints

Objectives	Endpoints (Outcome Measures)	IAP section
Primary		
To analyse the annualised relapse rate (ARR) yearly up to 5 years after cladribine tablet initiation.	Effectiveness: 
- ARR at 1, 2, 3, 4, 5 years after cladribine initiation.	14.1.1
Secondary		
To analyse the proportion of relapse-free patients at each year (and up to 5 years) after cladribine tablet initiation.	Effectiveness: 
- Number and % of relapse-free patients at 1, 2, 3, 4, 5 years after cladribine initiation.	14.2.1
To analyse the time after cladribine tablet initiation to first relapse.	Effectiveness: 
- Time to first relapse from cladribine initiation.	14.2.1

Objectives	Endpoints (Outcome Measures)	IAP section
To evaluate the proportion of patients who discontinued cladribine tablets and reasons for discontinuation.	Effectiveness: 
 - Number and % of patients who discontinued cladribine. - Number and % of reasons for discontinuation. 	14.2.2
To evaluate the subsequent disease modifying therapies (DMTs) received after cladribine tablets discontinuation up to 5 years after cladribine tablets initiation.	Effectiveness: 
 - Number of subsequent DMTs. - Number and % of patients who received subsequent DMTs. - Time to first subsequent DMT from last dose of cladribine. - Time to second subsequent DMT from last dose of cladribine. 	14.2.3
To analyse the proportion of patients with disability progression confirmed over 6 months, 2 years after treatment initiation.	Effectiveness: 
 - Change from baseline to year 2 in EDSS - Number and % of patients with disability progression confirmed over 6 months. 	14.2.4
To analyse the incidence of selected, identified, and potentially clinically important adverse events (AEs).	Safety: 
 - Number and % of patients with AEs - Number and % of patients with AEs by preferred term (PT) and system organ class (SoC). 	15.1
Others		
To evaluate MS-related lesions as assessed by MRI in patients with HDA-RRMS after cladribine tablet initiation.	Effectiveness: 
 - Number and % of patients with: 
 o T1 gadolinium enhancing lesions, o T2 new lesions, o T2 enlarging lesions. 	16.1

6 Overview of Planned Analyses

The final analysis will be performed once the study is completed with the purpose of evaluating all outcomes and the database is locked. The final analysis will include data collected during the first and the second chart abstractions. The database will be locked once the second chart abstraction is completed on all patients unless they withdrew consent, discontinued the study, or were lost to follow-up.

7 Changes to the Planned Analyses in the Clinical Study Protocol

There are no changes to the planned analyses in the clinical study protocol.

8 Analysis Sets and Subgroups

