## 9 Research Methods

### 9.1 Study Design

#### 9.1.1 Design Overview

This will be a multicentre chart review, Phase IV study, to be conducted across approximately 7 or 8 sites in the UK, using medical records of patients who initiated cladribine tablet monotherapy for treatment of HDA-RRMS per clinical practice. The observational chart review study design, allowing collection of real-world data dating back to product launch, will maximise the patient observation periods while minimising the burden for the sites and patients.

Patients with HDA-RRMS who initiated treatment with cladribine tablets and are fulfilling the other study eligibility criteria will be identified from patient records and asked to consent to participate in the study. Informed consent may be obtained at the site or remotely (additional details are provided in [Section 10.1](#)). Patients should have initiated treatment with cladribine tablets between 22 August 2017 (i.e., date of EU marketing authorisation of cladribine tablets) and at least 3 years before enrolling into the study. In addition, the patient should have completed at least Year 1 of cladribine treatment (i.e., 2 treatment weeks). Sites should aim to enrol patients in chronological order, based on the start date of treatment with cladribine tablets: i.e., patients who initiated cladribine tablets first will be contacted for enrolment first and their data should be abstracted first.

In this observational chart review study, the drug was prescribed before the patient was enrolled in the study as part of routine clinical practice and independent from participation in the current study.

[figure not shown]
The enrolment date is defined as the date of signing informed consent. Annual chart reviews will be based upon the date of cladribine tablet initiation, which is defined as the start date of Year 1 treatment with cladribine tablets as documented in patients' medical records. This study will involve 2 chart abstractions, with the first chart abstraction at the patient's enrolment and the second chart abstraction approximately 1 year after enrolment ([Figure 1](#)).

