The first chart review will take place after obtaining patients' consent to participate in this study. Patient data will be abstracted within 28 days after obtaining informed consent. The data will be abstracted from the medical chart and will include relevant medical history, data recorded in the year prior to cladribine tablet initiation, and data recorded between the date of treatment initiation with cladribine tablets and the study enrolment date ([Table 1](#) and [Section 9.3](#)). In addition, the patient's general practitioner may be contacted by the principal investigator or a member of the site team to obtain information regarding medical history and concomitant medications.

The second chart review will be conducted approximately 1 year after enrolment (within a window of 14 days from a year after the enrolment date). This second chart abstraction will collect data recorded between the enrolment date and the date of the second data abstraction ([Table 1](#) and [Section 9.3](#)).

The data to be collected are routinely collected information per clinical practice, including demographic data, disease characteristics (relapse reports, Expanded Disease Severity Scale [EDSS] scores, MRIs, and lymphocyte counts, as available), treatments (cladribine tablets, other DMTs for MS, and COVID-19 vaccines), medical history, and selected AEs.

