## **9.2.5 Withdrawal from the Study**

Patients are free to discontinue the study at any time without giving their reasons. In addition, patients can be withdrawn from the study for the following reason:

- Enrolment in an investigational clinical trial during the study period

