10.1 Disposition of Participants and Discontinuations

The following will be presented in a summary table by the most recent prior DMT and overall:

- Total number of participants screened

- Number of screened participants who discontinued from the study after screening will be summarised overall and grouped by the main reason for discontinuation:
 - Participant did not meet all eligibility criteria
 - Withdrew consent
 - Other
- Number of enrolled participants
- Number of patients in the Full analysis set (FAS)
- Number of patients in the FAS who completed study
- Number of patients by timing of the second chart review: The second chart review should be approximately 1 year from enrolment (365 calendar days \pm 14 calendar days).
 - Within the protocol-defined window
 - Outside the protocol-defined window
- Number of patients in the FAS who discontinued the study, with the primary reason of discontinuation:
 - AE
 - Death
 - Withdrawal by subject
 - Enrolment in an investigational clinical trial during the study period
 - Other [(COVID-19-related and COVID-19-non-related)]

Listings of discontinued participants will be provided. A listing of participants affected by the COVID-19-related study disruption by unique participant identifier will also be provided.

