15.1.1 All Adverse Events

The AEs will be summarised using the latest version of MedDRA PT as event category and MedDRA primary SOC body term as body system category.

Incomplete AE-related dates will be handled as specified in Section 9.10.

The following tables will be created:

- TEAE summary table with the number and percentage of patients that have:
 - TEAE
 - TEAE of Special Interest (TEAESI)
 - Grade 3 Lymphopenia
 - Grade 4 Lymphopenia
 - Herpes infections
 - Serious/opportunistic infections
 - Malignancies
 - TEAE leading to death

- TEAE leading to cladribine dose reduction
- TEAE leading to cladribine dose increase
- TEAE leading to cladribine temporary interruption
- TEAE leading to cladribine permanent discontinuation
- TEAE not recovered/resolved
- Any serious TEAE:
 - TEAESI
 - Leading to death
 - Leading to cladribine dose reduction
 - Leading to cladribine dose increase
 - Leading to cladribine temporary interruption
 - Leading to cladribine permanent discontinuation
 - Not recovered/resolved
- Cladribine-related TEAE:
 - TEAESI
 - Serious
 - Leading to death
 - Leading to cladribine dose reduction
 - Leading to cladribine dose increase
 - Leading to cladribine temporary interruption
 - Leading to cladribine permanent discontinuation
 - Not recovered/resolved
- The number and percentages of patients with TEAE by Primary SOC and PT
- The number and percentages of patients with TEAESI by Primary SOC and PT
- The number and percentages of patients with serious TEAE by Primary SOC and PT
- The number and percentages of patients with TEAE related to cladribine by Primary SOC and PT

TEAESI will be individuated using standardized and/or customized MedDRA queries that will be shared by Merck safety department using the dictionary version available at the time of the final analysis data-cut.

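### No chart abstraction is required up to the date of exit for patients who die, enter an investigational trial or otherwise discontinue after enrolment, so relapses and adverse events from that interval may go uncollected

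*SAP*

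**What the plan says.** Protocol 9.1.1 fixes the number of data collections: "This study will involve 2 chart abstractions, with the first chart abstraction at the patient's enrolment". After cladribine initiation, the first abstraction takes "data recorded between the date of treatment initiation with cladribine tablets and the study enrolment date". For the rest, "This second chart abstraction will collect data recorded between the enrolment date and the date of the second data abstraction"; its target is 365 days after enrolment, plus or minus 14. Table 1 of the protocol has no exit or early-termination review.

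SAP 6 builds the final analysis from these two abstractions. It sets the lock condition as the point when the "second chart abstraction is completed on all patients unless they withdrew consent, discontinued the study, or were lost to follow-up". Discontinuing the study is listed there separately from withdrawing consent.

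Protocol 9.2.5 permits withdrawal of a patient for "Enrolment in an investigational clinical trial during the study period". SAP 10.1 will tabulate the "Number of patients in the FAS who discontinued the study, with the primary reason of discontinuation", and the reasons listed are AE, death, withdrawal by subject, investigational trial and other.

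Protocol 11.2, by contrast, asks for any AE to be abstracted from cladribine initiation to the end of the study period and makes no exception for patients who leave.

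**The concern.** Take a patient who relapses in month 5 after consent and enters a trial in month 8. Consent stands and the chart holds the relapse, yet no scheduled step requires anyone to read it. The same applies to a patient who dies or leaves because of an AE.

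Two things are at stake. The first is the primary outcome. SAP 14.1.1 stops a patient's person-years at the date of last contact, and SAP 9.5 derives that date from recorded events and assessments. Without the second abstraction, follow-up would generally end near or before enrolment, so the unread relapse and its person-time both drop out. If leaving is linked to relapse, this censoring is informative, both for the annualised relapse rate (ARR) and for the relapse-free analysis in SAP 14.2.1. No sensitivity analysis addresses it.

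The second is safety. Protocol 9.9 notes that the eligibility criteria "limit the study population to patients who are alive at least 3 years after cladribine tablet treatment initiation". Every death the study can observe therefore falls after enrolment. SAP 15.1.1 plans a row for "TEAE leading to death", and its content depends on the data this gap exposes.

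**Working it through.** **1. Which data are exposed**

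- Initiation to enrolment (at least 3 years) comes from the first abstraction. Years 1 to 3 are therefore unaffected.
- Enrolment to about 1 year later comes from the second abstraction only. For a patient enrolled at exactly 3 years this is Year 4, and for one enrolled at 4 years it is Year 5. Protocol 9.2.3 allows at most 7 years: 1 before initiation, up to 5 to enrolment, and 1 after. For the latest enrollees, some or all of the post-enrolment year therefore lies beyond Year 5 and outside the ARR windows of SAP 9.6.
- AEs after Year 5 still count for safety.

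**2. The plan's own precision figure, as a yardstick**

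Protocol 9.5 gives a distance of 0.072 from the estimate to the 95% limit, for an expected ARR of 0.14 and 90 patients. The Wald formula for a proportion reproduces it:

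1.96 × √(0.14 × 0.86 / 90) = 0.0717, which rounds to 0.072.

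At 200 patients the same formula gives 0.048. This point does not dispute the figure.

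**3. Illustration of the ARR effect**

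The documents give no attrition rate, so the following are assumptions:

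- stayers relapse at 0.14 per year (Protocol 9.5; a 2-year figure, carried here to a later year);
- a share d leaves during the post-enrolment year and has no second abstraction;
- each leaver has 0.5 unobserved person-years and r unrecorded relapses;
- the reported rate is then the stayers' 0.14.

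True rate = [(1 − d) × 0.14 + d × r] / [(1 − d) + 0.5 × d]

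| d | r | Calculation | True ARR | Understatement |
|---|---|---|---|---|
| 2% | 0.07 | 0.1386 / 0.990 | 0.140 | 0 |
| 2% | 0.5 | 0.1472 / 0.990 | 0.149 | 0.009 |
| 2% | 1 | 0.1572 / 0.990 | 0.159 | 0.019 |
| 5% | 0.07 | 0.1365 / 0.975 | 0.140 | 0 |
| 5% | 0.5 | 0.1580 / 0.975 | 0.162 | 0.022 |
| 5% | 1 | 0.1830 / 0.975 | 0.188 | 0.048 |

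The rows with r = 0.07 (0.14 × 0.5) are leavers who relapse at the stayers' rate; there is no bias. Of 200 patients, 2–5% is 4 to 10 leavers, with 2 to 10 missed relapses at r of 0.5 to 1.

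These figures apply to post-enrolment person-time. A Year 4 or Year 5 rate that mixes both abstractions would shift less.

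**The case against.** The SAP 6 sentence is a condition for database lock. It says lock need not wait for leavers; it does not say their charts go unread, and it does not forbid abstraction up to exit. Withdrawal on trial entry is optional in Protocol 9.2.5. Protocol 11.2 asks for AEs to the end of the study period. The SAP also expects to know of deaths: death is a discontinuation reason (SAP 10.1), an event in the relapse-free analysis (SAP 14.2.1) and an end to the on-treatment period (SAP 9.7). Protocol 9.9 already names attrition as a limitation, and the study is descriptive, with no hypothesis test.

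Much of this stands, and it rules out three stronger readings that a reader might infer.

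- *The data are lost.* The documents are silent on abstraction to exit, so the supported statement is that the data may go uncollected.
- *All fatal AEs would be missing.* This assumes that no deceased patient's chart is read, which no text says. Death as a reason for leaving is recorded in any case. What is exposed is the detail: the event term, its onset and its course.
- *14–36% of post-enrolment relapses would be missed.* This divides 4 to 10 relapses by 0.14 × 200 = 28. It fixes the total at 28 while giving each leaver one relapse, which forces the stayers' rate down to (28 − 4)/196 = 0.122 or (28 − 10)/190 = 0.095. With stayers at 0.14 the shares are 4/31.4 = 13% and 10/36.6 = 27%. Even these rest on assumed exit rates and ignore the person-time that also drops out.

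The objection does not remove the gap. Protocol 11.2 covers AEs only, not relapses, subsequent DMTs or lymphocyte counts, and no scheduled abstraction implements it for a patient who has left. Naming attrition as a limitation does not recover data that sit in a readable chart.

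**Conclusion.** The concern holds as a gap in required data collection. Followed as written, the plan lets the database lock without reading the enrolment-to-exit interval for patients who discontinued while their consent stands, and this sits uneasily with Protocol 11.2.

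The effect on the ARR is conditional. It needs exits linked to relapse, which the documents neither state nor exclude, and it reaches only the part of Years 4 and 5 that falls after enrolment. Under the assumptions above (2–5% leaving, 0.5–1 unrecorded relapse and 0.5 unobserved person-years each), the understatement is 0.009 to 0.048. That is below the stated half-width of 0.072 at 90 patients; the upper end about equals the 0.048 half-width at 200. Unlike sampling error, it does not shrink as more patients are enrolled. The actual size cannot be computed from the documents.

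For safety, the details of fatal AEs are the data most exposed, because no death can be observed before enrolment. This is a cheap improvement worth making, not a flaw that invalidates the design.

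**What to change.** In Protocol 9.2.4 and 9.2.5 and in SAP 6:

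- Require the second abstraction at exit for every patient who leaves before Chart Review 2, has not withdrawn consent to data use, and has an accessible chart. It should cover enrolment to the date of exit, death or trial entry.
- End person-time at that date in SAP 14.1.1 and 14.2.1. SAP 9.5 needs a matching line, since it derives last contact only for participants not known to have died.
- Limit the lock exemption to withdrawn consent or an inaccessible chart.
- Reconcile Protocol 11.2 with SAP 6, so that the AE collection period and the abstraction schedule agree for patients who leave.

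The cost is a few abstractions done earlier than planned and a protocol wording amendment, which goes to the ethics committee if judged substantial (Protocol 9.10.1). SAP version 3.0 is dated 12 September 2023, in the quarter planned for the end of data collection and before the lock planned for Q4 2023. Charts can be read retrospectively, so the data remain obtainable until lock. The relapse and AE figures may come out slightly less favourable.
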